### **11 DRUG SUPPLIES**

Global Alliance for TB Drug Development will supply sufficient a quantity of the study drug, TBI-223 for preparation of TBI-223 oral suspension. Study drug will be shipped to Worldwide Clinical Trials Early Phase Services, LLC pursuant to site standard operating procedures. Upon receipt of the study drug, the study drug will be inventoried and stored in an environmentally controlled and secure, limited access area. The suspending vehicle and other supplies will be procured, inventoried, and stored appropriately by Worldwide Clinical Trials Early Phase Services, LLC pursuant to site standard operating procedures.

The lot numbers of the study drug, vehicle, and other supplies along with the expiration dates (where available) will be recorded and copies of the Certificate of Analysis (where available) will be maintained on file. Records will be maintained of the receipt and dispensation of the drugs supplied.

Samples will be collected from each batch of test product (TBI-223 Oral Suspension) and stored frozen until the clinical study report is issued. At the conclusion of the study, any unused study drug will be returned to the Sponsor or destroyed by the site pursuant to written authorization by the Sponsor and applicable federal and state regulations.

Global Alliance for TB Drug Development will supply sufficient quantity of the study drug, TBI-223 SR tablet formulations (Prototypes 1, 2, and 3) and TBI-223 IR tablet formulation for Part 2 of the study.

Study drug formulations will be shipped to Worldwide Clinical Trials Early Phase Services, LLC pursuant to site standard operating procedures. Upon receipt of the study drug products, the supplies will be inventoried and stored in an environmentally controlled and secure, limited access area. The lot numbers of the drugs along with the expiration dates (where available) will be recorded and copies of the Certificate of Analysis (where available) will be maintained on file. Records will be maintained of the receipt and dispensation of the drugs supplied. At the conclusion of the study, any unused study drug will be returned to the sponsor or destroyed by the site pursuant to written authorization by the sponsor and applicable federal and state regulations.

## **12 ADMINISTRATIVE ISSUES**

The Investigator is referred to the Investigator Brochure, or information provided during the study initiation visit, information provided by the study monitor, and ICH Guidelines for Good Clinical Practice for information regarding the study drug, details, or general considerations to be followed during the course of this study.

## 13 EVENTS SCHEDULE

**Table 9 Schedule of Assessments, Part 1**

STUDY DAY	SCR	CONFINEMENT																			FU	
		-28 to -2	-2 CI	-1	DAY 1										DAY 2					3	4	
					STUDY HOUR																	
EVENT		0	0.5	1	1.5	2	3	4	5	6	7	8	12	16 b	20	24	30	36	42	48	72	N/A
Informed consent and medical history	X																					
Height	X																					
Weight	X	X																				
Physical and neurological examinations c	X	X	X					X						X			X			X	X	
Vital signs (blood pressure, pulse, temperature, respiration rate, and pulse oximetry) d	X	X	X		X	X	X	X	X		X		X	X	X	X	X	X	X	X	X	
12-lead safety ECGs e	X	X	X f	X		X		X	X	X		X		X	X	X	X	X	X	X	X	
HIV/hepatitis B, C	X																					
Clinical laboratory tests (hematology, chemistry, and urinalysis)	X	X															X					X
Coagulation tests	X	X													X			X				X

STUDY DAY	SCR	CONFINEMENT																		FU				
		-28 to -2	-2 CI	-1	DAY 1										DAY 2				3	4	11 (+1) a			
EVENT					0	0.5	1	1.5	2	3	4	5	6	7	8	12	16 b	20	24	30	36	42	48	72
Urine drug, alcohol, cotinine screen	X	X																						
Serum pregnancy (females only)	X	X																						
FSH (post- menopausal females only)	X																							
Concomitant medication review	X																							
Check-in questions		X																						
Adverse events g	X	X		X		X		X	X	X		X		X	X	X	X	X	X	X	X	X	X	
High-fat, high- calorie breakfast (food-effect cohort only) h				X																				
Breath strip application i				X																				
Dose j				X																				
PK blood collection k				X	X	X	X	X	X	X	X	X	X	X	X	X	X	X	X	X	X	X	X	
Cardiac telemetry 12-lead Holter monitoring l																								
ECG extractions from Holter recording m			X	X*	X	X		X	X	X	X	X	X	X	X	X	X	X	X	X	X	X		

CI = check-in; ECG = electrocardiogram; FSH = follicle-stimulating hormone; FU = follow up; HIV = human immunodeficiency virus; N/A = not applicable; PK = pharmacokinetic; SCR = screening; T and R = temperature and respirations

- a. For the food-effect cohort, the timing of the Day 11 (+1) follow up phone call will be relative to Period 2 dosing.
- b. The 16-hour time point following dosing on Day 1 will either be on Day 1 or Day 2, depending upon time of dosing on Day 1.
- c. A detailed neurological exam will be conducted by a licensed physician or suitably medically qualified designee at both scheduled and unscheduled time points as deemed necessary by the Investigator. The neurological examination is planned to be performed around the estimated  $T_{max}$  (currently estimated at 3 hours post dosing; this time could change based on data generated during the study). Timepoints can be altered based on generated PK data.
- d. Vitals signs will be measured at screening, check-in, and while subjects are in confinement. Vitals signs will be measured within 90 minutes prior to dosing and within 15 minutes of the remaining defined time points in flowchart. Both blood pressure and heart rate (pulse) should be captured simultaneously. Blood pressure and heart rate should be measured after subjects are in a seated position for at least 2 minutes and then again after standing for 1 minute, except when they are supine or semi-reclined because of study procedures and/or AEs, or as deemed necessary by the Investigator.
- e. 12-lead safety ECGs will be printed and reviewed on-site by the Principal Investigator or designee. TriPLICATE ECGs will be completed at screening, Day -2, Day -1, and at 48 hours only. All other time points will be single ECG readings within 15 minutes at time points within flowchart. The predose ECG should be performed prior to the pre-dose blood draw. If a subject experiences a post-dosing QTcF  $>500$  msec or a change-from-baseline QTcF  $>60$  msec, after repeat testing, additional ECGs should be recorded until normalization or return to baseline.
- f. The first ECG may be done within 2 hours prior to dosing and must be completed 20 minutes prior to the pre-dose blood draw. All safety ECGs on Day 1 and Day 2 will be extracted from a continuous 12 lead Holter recording at discrete timepoints as noted in above flow chart and Day -1 will be extracted at the same time as vital sign measurements.
- g. Subjects will be monitored for treatment-emergent AEs from the time of dosing and throughout the study via safety assessments, observation, and subject reporting. A specific inquiry regarding AEs will be conducted prior to dosing and at time points determined by the Investigator postdose and upon return to clinic for subsequent visits. The inquiry to collect AEs using non-leading questions on Day 11 ( $\pm 1$  day) will be done via a phone call.
- h. In the fed treatment period of the food-effect cohort, a high-fat, high-calorie breakfast meal will be given 30 minutes before treatment administration.
- i. A breath strip will be added to the subject's tongue before and after dose administration in order to blind the subject to treatment.
- j. TBI-223 oral suspension and placebo for TBI-223 oral suspension will be administered orally followed by approximately 200 mL of water.
- k. Samples collected for plasma pharmacokinetic analysis will be processed per the instructions in Appendix 1.
- l. Cardiac telemetry will begin at least 24 hours before and end at least 48 hours after dosing.
- m. Replicate 12-lead ECGs will be extracted from a continuous Holter recording at discrete timepoints as noted on Day 1 in above flow chart for cardiodynamic assessment.

\*Three timepoints before dosing: -45, -30, and -15 minutes.

NOTE: When ECG extractions coincide with safety ECGs, vital signs assessments, and/or blood draws, then procedures should be carried out in said order.

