#### **6.5 Fasting/Meals/Beverages**

##### **6.5.1 Fasting/Meals**

Part 1 fasted cohorts and Part 2, Cohort 8, Arm 4 only Optional meals (lunch, snack, and dinner) may be served the day of check-in. All subjects will then be required to fast for at least 10 hours before dosing. The subjects will fast for 4 hours after dosing. Standard meals will be provided at appropriate times after dosing.

Part 1 food-effect cohort, Part 2, Cohort 8, Arms 1-3 and Cohort 9: Optional meals (lunch, snack, and dinner) may be served the day of check-in.

In the fasting study period, all subjects will be required to fast overnight for at least 10 hours before dosing.

In the fed study period of Part 1 and Part 2 (Cohort 8, Arms 1-3 and Cohort 9) subjects will be required to fast for at least 10 hours overnight before consuming a required FDA standard high-fat, high-calorie breakfast. Subjects will receive the required FDA standard high-fat, high-calorie breakfast to begin 30 minutes prior to scheduled administration of the dose and to end (last bite taken) within 5 minutes prior to dosing. The subjects will fast for 4 hours thereafter. The following high-fat (approximately 50% of total caloric content of the meal), high-calorie (approximately 1000 calories) breakfast will be ingested 30 minutes prior to administration of the drug:

- 2 eggs fried in butter
- 2 strips of bacon
- 2 slices of toast with butter
- 4 ounces of hash brown potatoes
- 8 ounces of whole milk

This meal contains approximately 150 protein calories, 250 carbohydrate calories, and 500-600 fat calories. An equivalent meal may be substituted with documentation of the menu and caloric contents with Sponsor approval prior to administration of the meal.

Subjects will fast for 4 hours after dosing. Standard meals will be provided at appropriate times after dosing.

Please note that Part 2, Cohort 9 is the same 6 subjects that were in Cohort 8 Arm 4 (IR tablet formulation) under fed conditions. In Cohort 8 Arm 4, subjects fasted.

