6.6.2 Administration of TBI-223 Oral Suspension or Placebo for TBI-223 Oral Suspension

*Note: Detailed instructions for preparing and dispensing TBI-223 will be provided in a separate pharmacy manual. Any instructions in the pharmacy manual shall supersede those presented in this protocol.*

TBI-223 Oral Suspension or placebo for TBI-223 oral suspension will be transferred and stored in Pyrex glass reagent bottles with a polypropylene (PP) screw cap without a liner. These bottles will be used for mixing, sampling, and storage prior to administration.

The required doses of the drug product will be dispensed using commercially available oral syringes of suitable capacity. The suspension will be dispensed just prior to dosing and not stored in the oral syringes.

Each dose of TBI-223 will be administered orally followed by approximately 200 mL of room temperature water. A mouth check will be performed immediately after dose to ensure that the medication has been appropriately swallowed.

Subjects will remain seated, except as otherwise required for study procedures or personal needs, for the first 4 hours after dosing. Should the need to move about occur during the first 4 hours after dosing on these days, subjects may be escorted to such procedures or activities by research personnel as deemed medically necessary. Subjects will not be allowed to lie down, except as directed by clinical staff secondary to AEs, for the first 4 hours after dosing.

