#### 6.9.7 Cardiac Holter Monitoring, and Cardiodynamic Assessment

In order to detect potential changes in ECG parameters, study subjects will undergo cardiac Holter monitoring. Holter monitoring will begin approximately 24 hours before dosing and continue for at least 48 hours after dosing.

On Day -2 and Day -1, subjects should fast until lunch to avoid circadian fluctuations.

In addition, replicate ECGs will be obtained after dosing, specifically around the estimated Tmax (which is estimated to be around 3 hours after dosing; although the timing may be altered based on generated phase 1 pharmacokinetic data). ECG data will be analyzed focusing in particular on changes of the QT segment although other ECG parameters will be analyzed, as specified in the Statistical Analysis Plan (SAP).

Continuous 12-lead ECGs (Holter) will be recorded for 24 hours prior to dose and for at least 48 hours post dose. The ECG waveforms will be stored for analysis as appropriate after the completion of the study. Replicate 12-lead ECGs will be extracted prior to dosing and serially after dosing by the central ECG laboratory at the time points shown in Table 9. At each time point for ECG extraction, subjects should be resting in the supine position for at least 10 minutes.

NOTE: When ECG extractions coincide with safety ECGs, vital signs assessment and blood draws, procedures should be carried out in said order.

Details regarding the equipment and methods to be used for continuous Holter extraction and analysis are provided in Appendix 4.

Part 2 of the study will not have cardiac Holter monitoring.

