### TQT Plus ECG Extraction Technique

Ten 14-second digital 12-lead ECG tracings will be extracted from the continuous Holter recordings using the “TQT Plus method”, a computer-assisted and statistical process utilized by iCardiac Technologies. The method enables extraction of ECGs with the lowest HR variability and noise within the protocol-specified extraction time window (e.g., the HR and QT changes from beat-to-beat in the range of <10%). At each protocol-specified timepoint, 10 ECG replicates will be extracted from a 5-minute “ECG window” (typically, the last 5 minutes of the 15-minute period when the subject is maintained in a supine or semi-recumbent quiet position).

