6.2.2 Baseline

Baseline is defined as the last non-missing value (either scheduled, unscheduled or repeat) before the subject receives the single dose of study drug in the relevant study part and dosing period.

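### In the fed period of the Part 1 food-effect cohort, the -15 minute pre-dose Holter extraction and its supine rest fall inside the high-fat breakfast, and the -30 minute extraction falls at its start

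*Protocol*

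**What the plan says.** The note to Table 9, the Part 1 schedule, attaches three pre-dose extraction times to the hour-0 entry: "Three timepoints before dosing: -45, -30, and -15 minutes". It gives no other times for the fed period of the food-effect cohort.

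Section 6.5.1 fixes the fed-period meal: "breakfast to begin 30 minutes prior to scheduled administration of the dose and to end (last bite taken) within 5 minutes prior to dosing". Note h to Table 9 agrees: "a high-fat, high-calorie breakfast meal will be given 30 minutes before treatment administration".

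Section 6.9.7 sets the resting condition: "At each time point for ECG extraction, subjects should be resting in the supine position for at least 10 minutes". Appendix 4 takes ten replicates from a 5-minute window, described as "typically, the last 5 minutes of the 15-minute period when the subject is maintained in a supine or semi-recumbent quiet position".

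Holter recording is waived for the capsule repeat cohort (Appendix 5) and for Part 2 (Section 6.9.7, Appendix 6), but not for the fed period. Section 6.4 admits food-effect subjects on Day -2 of both periods. The Table 9 note on the order of coinciding procedures covers safety ECGs, vital signs and blood draws; it does not mention the meal.

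On baseline, SAP Section 6.2.2 reads: "Baseline is defined as the last non-missing value (either scheduled, unscheduled or repeat) before the subject receives the single dose of study drug", applied by study part and dosing period. SAP Section 6.2.7 averages ECG values when several are recorded at one time point. Neither document says which pre-dose extractions form the Holter baseline.

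**The concern.** A subject cannot eat a required breakfast and lie quietly supine over the same minutes. Site staff following Section 6.5.1 would break Section 6.9.7, and the reverse. How each subject's conflict was settled would be a local decision that the data might not show.

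At stake is the fed-period change from baseline in heart rate and QTcF. Section 1.3 reports QT prolongation in dogs and Section 7.10 names increased heart rate as a preclinical finding, so these are the ECG variables that matter most. If the meal or posture shifts the pre-dose reading, every later change in that period carries the shift. The fasted and fed periods of the same subjects would then also start from different conditions. The protocol already controls food around the ECG on earlier days, since Section 6.9.7 has subjects fast until lunch on Day -2 and Day -1. The fed Day 1 has no matching provision.

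**Working it through.** The plan states no figure to reproduce. The check is the overlap of intervals, in minutes relative to dosing:

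overlap = max(0, earlier of the two ends - later of the two starts).

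Inputs:
- Extraction times: -45, -30, -15 (Table 9).
- Meal: -30 to -5, or -30 to 0 if the last bite is as late as allowed (Section 6.5.1).
- Supine rest: at least 10 minutes (Section 6.9.7); typically 15 minutes of quiet rest, with the last 5 as the reading window (Appendix 4).

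The documents do not say where the nominal time falls within the rest and window, so three placements are tried.

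| Nominal time marks | -45 | -30 | -15 |
|---|---|---|---|
| end of the window | rest -60 to -45: 0 | rest -45 to -30: 0; window 0 | rest -30 to -15: 15 of 15; window -20 to -15: 5 of 5 |
| start of the window | rest -55 to -45 and window -45 to -40: 0 | rest -40 to -30: 0; window -30 to -25: 5 of 5 | rest -25 to -15: 10 of 10; window -15 to -10: 5 of 5 |
| start of the 15-minute rest | rest -45 to -30: 0 | rest -30 to -15: 15 of 15; window -20 to -15: 5 of 5 | rest -15 to 0: 10 of 15 (meal ends -5) or 15 of 15 (meal ends 0); window -5 to 0: 0 or 5 of 5 |

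The results for the other cells are the same for either meal end.

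- **-45:** no overlap under any placement.
- **-30:** no overlap if the window ends at -30; the whole window overlaps under the other two placements.
- **-15:** conflict under every placement. If the rest precedes -15, all of it falls in the meal. If the rest starts at -15, at least 10 of its 15 minutes do, although the window itself escapes when the meal ends at -5.

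Share of the baseline affected:
- mean of the three: 1/3 (only -15) to 2/3 (-30 and -15);
- last value only: all of it, since -15 is the last.

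Check of the proposed times -75, -60, -45: the latest any rest can end is -45 + 15 = -30, the start of the meal, so overlap is 0 under every placement. The earliest rest starts at -75 - 15 = -90, against -45 - 15 = -60 now, which is 30 minutes earlier.

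**The case against.** The strongest reply is that the gap is narrow. Only -15 conflicts under every reading, -45 is always clear, and the fasted baselines used for dose escalation are untouched. That stands.

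A reader might infer that the SAP's last-value rule makes the -15 reading the fed baseline. The documents do not show this. The cardiac vendor and core laboratory read the extractions (Section 6.2.5, Appendix 4), and SAP Section 6.12.5 lists only Holter collection data. The three times share one hour-0 entry, so SAP Section 6.2.7 could equally be read as averaging them. The pre-dose safety ECG may be done up to 2 hours before dosing and so can precede the meal. What remains is that no baseline is defined for these readings.

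A reader might also put a size on the QTcF error. With QT held at 400 ms, QTcF = QT / RR^(1/3) gives 400 at 60 bpm and 410.8, 421.1 and 430.9 at 65, 70 and 75 bpm. But the 5 to 15 bpm rise is an assumption, the meal posture is not stated, and holding QT fixed assumes no adaptation at all; with full adaptation the error is 0. Appendix 4 also selects stable stretches and reviews beats where QT or RR changes rapidly. These figures are not an estimate.

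The cohort has 2 placebo subjects with the same fed schedule, and SAP Section 6.3 gives fed placebo its own column. A shared error would show there, but two subjects give little to correct with.

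Finally, Table 2 is headed as actual cohorts and the SAP names Cohort 5 (1200 mg) as the food-effect cohort, so the fed period may already have been dosed. That changes the remedy but does not remove the problem.

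**Conclusion.** The point holds in a limited form. As written, the fed-period schedule cannot be followed at -15 minutes, and may not be at -30, depending on where the nominal time sits in the reading window. One, possibly two, of the three pre-dose readings would be taken during a meal and not at supine rest, in each of the 10 planned food-effect subjects (8 active, 2 placebo). This can distort fed-period change from baseline in heart rate and QTcF. Neither the size nor the effect on a reported result can be derived: the documents give no meal effect, no Holter baseline rule and no cardiodynamic model.

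This rests on Table 9 applying unchanged to the fed period, which follows from Holter being waived only elsewhere.

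A separate matter is wording only. Section 6.6.2 says "Subjects will not be allowed to lie down, except as directed by clinical staff secondary to AEs, for the first 4 hours after dosing", and Section 6.6.3 repeats it for tablets, while Sections 6.9.6 and 6.9.7 require supine ECGs, including around 3 hours after dosing in Part 1. A reader might infer that post-dose ECGs are barred. Section 6.9.3 and Table 9 note d, however, foresee subjects being supine for study procedures, so the intent is clear enough.

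**What to change.** - **Table 9:** add fed-period pre-dose extraction times such that all three, with their supine rest, finish before the first bite, for example -75, -60 and -45 minutes. State where the nominal time falls within the rest and the 5-minute window.
- **SAP:** state that the fed-period Holter baseline is the mean of the pre-meal extractions.
- **If the fed period has been dosed:** re-extract pre-meal windows from the stored recording where supine rest is documented, or use the -45 minute point. Holter runs from about 24 hours before dosing and waveforms are kept (Section 6.9.7), so no new procedure is needed.
- **Wording:** reconcile the 4-hour lying-down restriction in Sections 6.6.2 and 6.6.3 with the supine ECG requirements in Sections 6.9.6 and 6.9.7.

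The cost is a footnote, a SAP sentence and a wording correction. Supine rest starts about 30 minutes earlier in the fed period. A pre-meal baseline also means that fed-period change from baseline includes any effect of the meal itself. It should be read against the fed placebo subjects, with the caution that two subjects require.

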## APPENDIX 1 PHARMACOKINETIC SAMPLE PROCESSING

### A. Collection and Processing

A more detailed description of plasma sample preparation requirements may be provided by the analytical laboratory. If such a description is provided, the method of sample preparation provided by the laboratory shall supersede those provided in this protocol and appropriate documentation shall be placed in the Investigator Site File (ISF).

Processing Instructions	
1	Samples will be collected via direct venipuncture at the time points delineated in the appropriate Events Schedule (Section 13).
2	Blood will be drawn into pre-chilled 4 mL evacuated tubes containing K 3 -EDTA and immediately placed on wet ice and then processed to plasma within 60 minutes.
3	Samples will be centrifuged at 1500 g at approximately 4°C (± 10 degrees) for 10 minutes. After centrifugation, two aliquots of plasma (the first containing at least 0.5 mL and the second containing the remainder of the plasma) will be removed and placed in appropriately labeled 5 mL polypropylene vials.
4	The aliquots will be immediately placed on dry ice. Within 90 minutes of collection, the aliquots will be stored in a freezer set at -20°C ± 10°C and remain in the freezer until transferred for analysis.
5	Samples will be transferred at the agreed upon intervals.
6	The aliquots will be transferred on dry ice to the Alliance Pharma, Inc. bioanalytical laboratory for the determination of plasma concentrations of TBI-223 and TBI-223 M2, using a validated procedure at Alliance Pharma.
7	Blood sampling, plasma processing, and storage time will be documented in the study records.

